7.6.1 Treatment Overdose

For this study, any dose of rezafungin greater than the stipulated dose will be considered an overdose.

In the event of an overdose, the Investigator should:

- Contact the medical monitor immediately.
- Closely monitor the subject for any AE/SAE and laboratory abnormalities until resolution, stabilisation of the event, the event is otherwise explained, or the subject is lost to follow-up.
- Obtain an additional blood sample for PK analysis if requested by the medical monitor (to be determined on a case-to-case basis).
- Document the quantity of the excess dose as well as the duration of the overdose.

7.7 Concomitant Therapy

Any medication taken by the subject or administered to the subject other than the IP specified in the protocol (including medication administered for treatment of AEs) is considered concomitant medication. Information about concomitant medications will be recorded in the eCRF from the Screening visit until Follow-up (Day 30 ± 5 days).

Administration of any other antifungal medication classified as an azole or polyene (as standard-of-care), will be allowed.

Using a concomitant echinocandin as the standard-of-care, or having received an echinocandin within 5 days before planned dosing with rezafungin, is not permitted in the study. However, if following dosing with rezafungin, a subject requires the administration of another echinocandin due to medical needs judged by the Investigator, it will be allowed after at least 7 full days after dosing with rezafungin.

Medications that are ongoing at study entry (after the informed consent) and any medication given to the subjects during the study (after the informed consent) through the last study evaluation (Follow-up [Day 30 ± 5 days]) must be recorded on the source documents and appropriate section of the eCRF. The use of any concomitant medication must relate to an AE or the subject's medical history. The medication must be recorded with:

Reason for use

Dates of administration including start and end dates

Dosage information including dose, frequency, and route of administration

The medical monitor should be contacted if there are any questions regarding concomitant or prior therapy.

7.7.1 Rescue Medication

For the purpose of this study, there is no specific rescue medication.

8 DISCONTINUATION OF STUDY TREATMENT AND SUBJECT DISCONTINUATION/ WITHDRAWAL

8.1 Discontinuation of Study Treatment

This is a single-dose study. All subjects enrolled will receive a single infusion of IP (rezafungin).

Stopping Rules

Stopping Criteria for an Individual Subject

- In case of any systemic reaction (i.e., cytokine release syndrome, including nausea, headache, tachycardia, hypotension, rash, and/or shortness of breath) or local infusion-related reaction (i.e., injection site pain or tenderness, erythema or redness, induration or swelling, or pruritis) with a severity of Grade 2 or higher (according to the DAIDS criteria, Version 2.1), the infusion will be immediately stopped and not restarted, and treatment provided as appropriate. The date and time of discontinuation must be recorded in the eCRF. The Sponsor/medical monitor must be informed immediately (no later than 24 hours of Principal Investigator's knowledge of the event). Where feasible, the PK assessment will continue if the subject is well enough and willing to continue.
Note: in case of Grade 1 local reactions, the investigator may slow down the infusion or temporarily discontinue the infusion (see Section 7.6).
- A subject becomes pregnant.

Criteria for Pausing or Stopping the Study

The study would be paused in cases where:

- One subject experiences a serious unexpected adverse event that is considered at least possibly related to rezafungin. The event will be investigated and the causality established before dosing the next available subject.

The study would be stopped in cases where any of the following occurs:

- A study drug-related significant adverse reaction (i.e., a serious AE considered at least possibly related to the IP administration) leading to treatment discontinuation in 2 subjects
- Two or more subjects have experienced a Grade ≥ 4 AE considered to be related to rezafungin
- The Investigator and the Sponsor both agree that the tolerability profile is unacceptable, based on the frequency and intensity of observed AEs (including serious and related AEs)
- At the request of the DSMB, based on a safety concern during the review of the safety and tolerability data

- Additional data from other clinical trials or toxicological studies become available that negatively influence the risk/benefit assessment
- At a specific site/in a specific region: if the local regulatory authority or Independent Ethics Committee (IEC) withdraws approval of the study

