Infusion-related reaction monitoring (collected as AEs)			x	x	x	x			

AE=adverse event; BMI=body mass index; ECG=electrocardiogram; ET=early termination; ICU=intensive care unit; IP=investigational product; IV= intravenous; PK=pharmacokinetics; SAE=serious AE.

Note: When coinciding with each other, ECGs, vital signs, and pharmacokinetic blood collections should be performed in said order.

* BMI=kg/m² where kg is a subject's weight in kilograms and m² is their height in metres squared ([Appendix 6](#)).

- a. ET assessments can be performed at the time of discontinuation. In case of ET, the reason for discontinuation must be documented.
- b. Written parental (or appropriate legal representative) informed consent and/or age-appropriate assent/consent.
- c. Record whether the subject is in the general ward or ICU. If the subject is in the ICU, record the Paediatric Index of Mortality 2 (PIM2) variables ([Appendix 7](#)).
- d. All medication taken up to 7 days prior to the informed consent, medication ongoing after the informed consent, and all medication given to the subjects during the study until Follow-up (Day 30 ± 5 days) must be recorded.
- e. A complete physical examination is to be performed at Screening and Follow-up. At all other time points, a brief targeted examination is to be performed as clinically indicated, driven by the subject's symptoms and signs. A complete and brief targeted physical examination will include, at a minimum, assessments of the cardiovascular, respiratory, gastrointestinal, and central and peripheral neurological systems.
- f. Vital signs will be taken after subject is sitting or supine for at least 5 minutes and will include temperature, pulse rate, respiratory rate, and blood pressure. On the day of dosing (Day 1) vital signs will be taken predose, 15-30 minutes after the start of IP infusion, and 30-60 minutes after the completion of IP infusion.
- g. Clinical laboratory tests (haematology, biochemistry, urinalysis): The following tests will be performed at Screening and at Follow-up: Complete blood count, alkaline phosphatase (ALP), blood urea nitrogen (BUN), alanine aminotransferase (ALT), aspartate aminotransferase (AST), total and conjugated bilirubin, creatinine, total protein and albumin, glucose (fasting or non-fasting), potassium, sodium, calcium (see [Appendix 2](#) for details).
- h. 12-lead ECG: at Screening and between 3 and 4 hours after start of IP infusion on Day 1.

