8.2 Subject Discontinuation/Withdrawal from the Study

Participation in the study is strictly voluntary.

- A subject has the right to withdraw from the study at any time for any reason.
- The subject's parent(s)/LAR (as applicable) may choose to withdraw the subject from the study at any time or the subject may be withdrawn at any time at the discretion of the Investigator for safety (due to AEs or SAEs), or compliance reasons.
- At the time of discontinuation from the study, if possible, an ET visit should be conducted, as shown in the SoA. For data to be collected at the time of study discontinuation see SoA ([Table 1](#) and [Table 2](#)). The subject will be permanently discontinued from the study treatment and the study at that time.
- If the subject or subject's parent(s)/LAR withdraws consent for disclosure of future information, the Sponsor may retain and continue to use any data collected before such a withdrawal of consent.
- If a subject withdraws from the study, he/she or the subject's parent(s)/LAR may request destruction of any samples taken and not tested, and the Investigator must document this in the source documents and relevant medical records. Samples not yet tested at the time of destruction request will be destroyed.
- The reason for withdrawal will be recorded in the eCRF.

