9.2.2 Time Period and Frequency for Collecting AE and SAE Information

All AEs/SAEs will be collected from the start of IV infusion until the Follow-up visit at the timepoints specified in the SoA (see [Table 1](#) and [Table 2](#)).

Medical occurrences that begin before the start of study treatment but after obtaining informed consent will be recorded as medical history/current medical conditions, not as AEs.

All SAEs will be recorded and reported to the Sponsor or designee immediately and under no circumstance should this exceed 24 hours from the time of awareness, as indicated in [Appendix 3](#). The Investigator will submit any updated SAE data to the Sponsor within 24 hours of it being available.

Investigators are not obligated to actively seek information on AEs or SAEs after conclusion of the study participation. However, if the Investigator learns of any SAE, including a death, at any time after a subject has been discharged from the study, and he/she considers the event to be reasonably related to the study treatment or study participation, the Investigator must promptly notify the Sponsor.

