9.2.6 Adverse Event of Special Interest

In addition to SAEs, the following are considered an adverse event of special interest (AESI) and should be promptly reported to the Sponsor within 24 hours of awareness through the Reporting of SAEs process as defined in [Appendix 3](#), even if the nature of the AE is deemed non-serious according to the usual regulatory criteria.

Infusion-related reactions

Events that, in the opinion of the Investigator, may represent intolerance of the IV infusion of the IP. In general, these events would be temporally associated with the IV infusion of the Sponsor's IP.

Phototoxicity

Due to results from a nonclinical phototoxicity study in rats and a Phase 1 clinical trial indicating that rezafungin causes an increased risk for phototoxicity, classified as mild, subjects should be advised to avoid sun and other UV light exposure without adequate protection from Day 1 to Day 8 (i.e., including 7 days after the administration of rezafungin). Investigators should report any AE potentially related to or suspicion of phototoxicity to the Sponsor.

Neurological manifestations (such as ataxia, tremor and neuropathy)

In a rezafungin 3-month toxicity study in monkeys, there were observations of tremors, and histology with Schwann cell hypertrophy/hyperplasia (reversible) and phospholipidosis in the dorsal root ganglia first appearing at Week 6 of dosing and at 9.2-fold the exposure to the dosing regimen of rezafungin used in the Phase 3 pivotal study. Ataxia, axonal neuropathy, hypoesthesia, hyperesthesia, paraesthesia, peripheral neuropathy (motor, sensory, or sensorimotor), polyneuropathy, toxic neuropathy, and tremors will be considered AESIs.

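### Stop criterion 1 in Section 8.1 counts a related SAE only if it ends the 2-hour infusion, so repeated expected related SAEs of Grade 1 to 3 after the infusion reach no numeric rule

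*Combined protocol and SAP*

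**What the plan says.** Section 8.1 sets one numeric pause and two numeric stops.

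- **Pause:** "One subject experiences a serious unexpected adverse event that is considered at least possibly related to rezafungin". The event is investigated and causality settled before the next subject is dosed.
- **Stop criterion 1:** a significant drug-related reaction, defined as "a serious AE considered at least possibly related to the IP administration) leading to treatment discontinuation in 2 subjects".
- **Stop criterion 2:** two or more subjects with a rezafungin-related AE of Grade 4 or higher.

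The remaining stops carry no count. In criterion 3 the Investigator and Sponsor agree that tolerability is unacceptable, "based on the frequency and intensity of observed AEs (including serious and related AEs". The others are a DSMB request, new external data, and withdrawal of approval at a site or in a region.

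The same section opens with "This is a single-dose study. All subjects enrolled will receive a single infusion of IP (rezafungin"). In its individual stopping criteria, discontinuation means that the infusion is stopped and not restarted. Section 8.2 uses the word more widely for a child who withdraws: "The subject will be permanently discontinued from the study treatment and the study at that time".

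Section 9.2.2 sets the observation window: "All AEs/SAEs will be collected from the start of IV infusion until the Follow-up visit", that is, Day 30 ± 5 days. Appendix 3 treats seriousness and severity as separate, so an SAE can be Grade 1, 2 or 3.

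**The concern.** Ending treatment is a natural condition in a repeat-dose trial, where a child who reacts badly is taken off the drug. Here the drug has already been given once the two hours are over. An SAE that starts later cannot end a finished infusion, however clearly it is related.

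The wider use in Section 8.2 offers a way round this, but a poor one. If leaving the study counts as treatment discontinuation, the safety count depends on which families withdraw. Two children with the same event would be counted differently according to whether they stayed in follow-up.

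The protocol itself looks for events after the infusion. Tables 1 and 2 both list "Infusion-related reaction monitoring (collected as AEs"), which runs to the 6 to 8 hour visit in Groups 1 to 3 and to the 24 hour visit in Group 4. For phototoxicity, an event of special interest, "subjects should be advised to avoid sun and other UV light exposure without adequate protection from Day 1 to Day 8".

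At stake is whether a fixed count would halt dosing if such events recurred. This matters most in two places. In Part 2, 16 children (up to 20) are enrolled in two parallel groups, and dosing continues during DSMB review 2. In Part 3, Group 4 is dosed after all three scheduled DSMB reviews (Section 10.6).

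**Working it through.** **Step 1: test each rule against one event class.** The class is an SAE, at least possibly related, starting after the infusion, Grade 1 to 3.

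| Rule in Section 8.1 | Unexpected | Expected |
|---|---|---|
| Pause at one subject | Yes, each time, with no cumulative count | No |
| Stop 1 (ends treatment, 2 subjects) | No, unless withdrawal is read in | No, unless withdrawal is read in |
| Stop 2 (Grade ≥4, 2 subjects) | No | No |
| Criterion 3; DSMB request | Judgement, no number | Judgement, no number |

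The bottom right cell is the gap. This result is logical and needs no event rate.

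**Step 2: share of the window in which criterion 1 can act.** Day 1 to Day 25–35 is 24 to 34 elapsed days, or 24 × 24 = 576 h to 34 × 24 = 816 h. The infusion covers 2/816 = 0.25% to 2/576 = 0.35%. This is a share of time, not of risk.

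**Step 3: illustration.** The plan states no paediatric SAE rate and no operating characteristics for its rules, so there is no figure to reproduce. Assume:

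- *p*: chance per child of an SAE in this class (1%, 2%, 5%, 10%);
- *f*: share of these that is expected (5%, 25%, 50%, 100%);
- independence between children, and *q* = *f* × *p*.

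Then P(at least 2 of *n*) = 1 − (1 − *q*)^*n* − *n* *q* (1 − *q*)^(*n* − 1).

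Example: *p* = 5%, *f* = 50%, *n* = 16 gives *q* = 0.025 and 1 − 0.6669 − 16 × 0.025 × 0.6840 = 0.059.

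| *f* | *n* = 16 (Part 2), *p* = 1 / 2 / 5 / 10% | *n* = 32 (all), *p* = 1 / 2 / 5 / 10% |
|---|---|---|
| 5% | <0.1 / <0.1 / 0.1 / 0.3% | <0.1 / <0.1 / 0.3 / 1.1% |
| 25% | 0.1 / 0.3 / 1.7 / 5.9% | 0.3 / 1.1 / 6.1 / 19.0% |
| 50% | 0.3 / 1.1 / 5.9 / 18.9% | 1.1 / 4.1 / 19.0 / 48.0% |
| 100% | 1.1 / 4.0 / 18.9 / 48.5% | 4.1 / 13.4 / 48.0 / 84.4% |

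The last row is an upper bound: it equals the chance for all SAEs in the class, including unexpected ones that already pause the study. If *f* is zero, every entry is zero.

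**The case against.** The strongest case against is that the uncovered class is very narrow. An event must be serious, related, post-infusion, below Grade 4 and expected, all at once. For unexpected events the one-subject pause is stricter than any two-subject count, and Appendix 1 adds a decision on whether enrolment may resume. Section 3.3 names two kinds of AE associated with rezafungin: infusion-related reactions and phototoxicity. It describes phototoxicity as mild and does not call the two adult Phase 3 cases of infusion intolerance serious. The expected share may be close to zero. All of this stands.

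It also stands that criterion 1 does a real job. It fits the individual rule that stops the infusion for a reaction of Grade 2 or higher, and Section 3.3 links polysorbate 80 toxicity to peak concentration. A reader might infer from the 0.25% to 0.35% in Step 2 that the criterion is close to inoperative. The documents do not support that, because acute reactions may cluster in those two hours.

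The probabilities also overstate what a halt could prevent, since the second case may fall in the last child dosed. Among the first 8 children, at *p* = 5% and *f* = 50%, the chance is 1.6%, not 5.9%.

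Finally, leaving expected, non-life-threatening events to judgement is defensible, with 24-hour reporting of SAEs and events of special interest, Sponsor screening for pause or stop events, and DSMB review. The DSMB charter is not among the documents and may hold further triggers. These layers lower the importance, but none that the protocol describes supplies a count for the gap.

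**Conclusion.** The point holds in a limited form. Criterion 1 counts related SAEs that end the infusion. Related SAEs of Grade 1 to 3 after the infusion have no numeric cumulative rule, and for expected ones there is no numeric rule at all. That conclusion follows from the wording of Section 8.1, provided that discontinuation has its Section 8.1 meaning; under the Section 8.2 meaning, the count would depend on withdrawal from the study.

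The importance is minor to moderate. The size of the gap cannot be fixed from the documents, because they do not say whether any SAE is expected and give no paediatric rate. The tabulated probabilities show how the answer moves with assumed values and are not estimates of risk.

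A reader might infer that children with delayed SAEs are unprotected. The documents do not support this: the one-subject pause, the Grade 4 rule, criterion 3 and the DSMB all act on such events in part.

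**What to change.** In the substantial amendment already planned before Part 2, keep criterion 1 as a stop for SAEs that end the infusion, so that the existing stop is not softened. Add to the pausing criteria:

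*Two subjects experience an SAE at least possibly related to rezafungin, expected or not, with onset from the start of infusion to the Follow-up visit. Dosing is paused until the DSMB has reviewed the events and decided whether enrolment may resume. After resumption, each further such subject triggers a new review.*

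The one-subject pause, the Grade 4 rule and criterion 3 stay unchanged. The DSMB charter should carry the same text.

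The drafting cost is one short paragraph in each document. The operating cost is occasional extra pauses: under Appendix 3, an event is possibly related when the drug is one of several plausible causes, which will be common in ill children. From post-infusion SAEs below Grade 4 alone, at the assumed *p* of 1%, 2%, 5% or 10%, the new rule would be met with probability 4.1%, 13.4%, 48.0% or 84.4% over 32 children, and 6.1%, 19.0%, 60.1% or 92.0% over 40. These figures overstate the added burden, because unexpected events already pause dosing at the first subject. The extra pauses come mainly from expected events, and each can end with enrolment resuming.

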8.2 Subject Discontinuation/Withdrawal from the Study

Participation in the study is strictly voluntary.

- A subject has the right to withdraw from the study at any time for any reason.
- The subject's parent(s)/LAR (as applicable) may choose to withdraw the subject from the study at any time or the subject may be withdrawn at any time at the discretion of the Investigator for safety (due to AEs or SAEs), or compliance reasons.
- At the time of discontinuation from the study, if possible, an ET visit should be conducted, as shown in the SoA. For data to be collected at the time of study discontinuation see SoA ([Table 1](#) and [Table 2](#)). The subject will be permanently discontinued from the study treatment and the study at that time.
- If the subject or subject's parent(s)/LAR withdraws consent for disclosure of future information, the Sponsor may retain and continue to use any data collected before such a withdrawal of consent.
- If a subject withdraws from the study, he/she or the subject's parent(s)/LAR may request destruction of any samples taken and not tested, and the Investigator must document this in the source documents and relevant medical records. Samples not yet tested at the time of destruction request will be destroyed.
- The reason for withdrawal will be recorded in the eCRF.

8.3 Lost to Follow-up

A subject will be considered lost to follow-up if he/she repeatedly fails to return for the scheduled Follow-up visit and is unable to be contacted by the study site.

The following actions must be taken if a subject fails to return to the clinic for a required study visit:

- The site must attempt to contact the subject or the subject's parent(s)/LAR and ascertain whether the subject wishes to and/or should continue in the study.
- Before a subject is deemed lost to follow-up, the Investigator or designee must make every effort to regain contact with the subject or the subject's parent(s)/LAR (where possible, 3 telephone calls, and if necessary, a certified letter to the subject's last known mailing address or local equivalent methods). These contact attempts should be documented in the subject's medical record.

- Should the subject or the subject's parent(s)/LAR continue to be unreachable, he/she will be considered to have withdrawn from the study.

9 STUDY ASSESSMENTS AND PROCEDURES

Study procedures and their timings are summarised in [Table 1](#) and [Table 2](#).

Any safety concerns should be discussed with the Sponsor immediately upon occurrence or awareness to determine if the subject should continue or discontinue study treatment.

Adherence to the study design requirements, including those specified in the SoA, is essential and required for study conduct.

All Screening evaluations must be completed and reviewed to confirm that potential subjects meet all eligibility criteria. The Investigator will maintain a Screening log to record details of all subjects screened and to confirm eligibility or record reasons for screen failure, as applicable.

Investigations conducted as part of the subject's routine clinical management (e.g., blood count) and obtained before signing of the ICF may be utilised for Screening or baseline purposes provided the investigations meet the protocol-specified criteria and were performed within Day -3 to Day -1.

Blood samples for plasma PK determination (rezafungin plasma levels) will be collected in all subjects.

Repeat or unscheduled samples may be taken for safety reasons or for technical issues with the samples.

The blood volume for PK and other laboratory tests will not exceed the volume limits recommended by the EU paediatric guidance²¹ (up to approximately 3% of total weight [2.4 mL blood/kg body weight], with no more than 1% [0.8 mL blood/kg body weight] at any single time).

For subjects <2 years of age (Group 4), a maximum total of 1 mL of blood will be taken for PK sampling.

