- i. The IP will be administered as a single IV infusion over a period of 2 hours (± 5 minutes). The formulation used for Group 1 will be same as the one used in the adult clinical trials. For Group 2 and Group 3, a paediatric specific formulation that is currently under development will be used.
- j. Continuous vital sign and ECG monitoring will begin with start of IP infusion until completion of infusion.
- k. PK blood samples will be collected at the following 5 timepoints: at end-of-infusion ± 15 minutes, then between 3 and 4 hours after start of infusion, between 6 and 8 hours after start of infusion, at 48 hours (± 4 hours) after start of infusion (Day 3), and at 168 hours (± 12 hours) after start of infusion (Day 8). In cases where a subject is discontinued before all PK samples have been collected (Day 8), a last PK sample may be collected at the time of discontinuation if the subject and/or his/her parent(s)/legally authorised representative consents. The exact date and time of the PK samples must be recorded.

Table 2 Schedule of Assessments for Part 3 (Group 4: birth to <2 Years)

Study Period	Screening	Dosing		PK Sampling Postdose			Follow-up / ET ^a
Study Day	Day -3 to Day -1	Day 1		Day 1	Day 2	Day 8	Day 30 ± 5 Days
Procedure		Predose	Single IV infusion of rezafungin	end-of-infusion ± 15 mins	24 hrs ± 4 hrs after start of infusion	168 hrs ± 12 hrs after start of infusion	
Informed consent (parental consent/LAR) ^b	x						
Assess inclusion/exclusion criteria	x						
Demographics (age, sex, race, gestational age, and birth weight)	x						
Baseline characteristics (height, weight, and disease characteristics [indication for antifungal prophylaxis/treatment])	x						
Hospitalisation status at screening (general ward/ICU) ^c	x						
Medical/surgical history and current medical conditions	x						
Prior and concomitant medication use ^d	x	x	x	x	x	x	x
Physical examination ^e	x	x	x	x	x	x	x
Vital signs (temperature, pulse rate, respiratory rate, and blood pressure) ^f	x	x	x ^f	x ^f	x	x	x

Study Period	Screening	Dosing		PK Sampling Postdose			Follow-up / ET ^a
Study Day	Day -3 to Day -1	Day 1		Day 1	Day 2	Day 8	Day 30 ± 5 Days
Procedure		Predose	Single IV infusion of rezafungin	end-of-infusion ± 15 mins	24 hrs ± 4 hrs after start of infusion	168 hrs ± 12 hrs after start of infusion	
Clinical laboratory tests (haematology, biochemistry, urinalysis) ^g	x						x
12-lead ECG ^h	x				x		
IP administration ⁱ			x				

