- g. Clinical laboratory tests (haematology, biochemistry, urinalysis): The following tests will be performed at Screening and at Follow-up: Complete blood count, alkaline phosphatase (ALP), blood urea nitrogen (BUN), alanine aminotransferase (ALT), aspartate aminotransferase (AST), total and conjugated bilirubin, creatinine, total protein and albumin, glucose (fasting or non-fasting), potassium, sodium, calcium (see [Appendix 2](#) for details). Glucose can be measured by point-of-care testing to minimise the blood volume taken for the clinical laboratory tests if the point-of-care glucose meter is calibrated regularly as per the site's standard operating procedure.
- h. 12-lead ECG: at Screening and at 24 ± 4 hours after start of IP infusion (Day 2).
- i. The IP will be administered as a single IV infusion over a period of 2 hours (± 5 minutes).
- j. Continuous vital sign and ECG monitoring will begin with start of IP infusion until completion of infusion.
- k. PK blood samples will be collected at the following 3 timepoints: at end-of-infusion ± 15 minutes, at 24 hours ± 4 hours (Day 2) after start of infusion, and at 168 hours ± 12 hours (Day 8) after start of infusion. In cases where a subject is discontinued before all PK samples have been collected (Day 8), a last PK sample may be collected at the time of discontinuation if the subject and/or his/her parent(s)/LAR consents. The exact date and time of the PK samples must be recorded. A maximum total of 1 mL of blood will be taken for PK sampling.

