After completion of the Follow-up visit for all subjects in Group 1, there will be an interim review of the safety, tolerability, and PK data. The data will be reviewed by the Data Safety Monitoring Board (DSMB) to ensure that the exposure achieved in subjects from this group is safe and well tolerated. This will allow for a decision to proceed to Part 2.

In parallel to this study a formulation development programme is being undertaken to identify a lower strength paediatric specific formulation with an appropriate PS80 level for use in subjects <12 years of age. A lower strength formulation (e.g., 100 mg/vial, compared with 200 mg/vial for the formulation used in Group 1) would reduce the risk of a 10-fold overdose in children with a weight of <3 kg. Once the paediatric formulation is available for use, after completion of Part 1, the study will be paused and a substantial amendment will be submitted to enable use of the paediatric formulation in Part 2 and Part 3 (for dosing in subjects <12 years of age).

Part 2

Enrolment for Part 2 (subjects aged 2 to <12 years) will commence after safety has been confirmed by the DSMB and the paediatric formulation has been identified and ready to be used. The dose for this age group is planned to be 4 mg/kg (not to exceed a total dose of 200

Formatte

Color(RG

Formatte

Custom C
grammar

mg). The dose and PK sampling timepoints may be adjusted as appropriate after assessment of the PK and safety data of Part 1.

The study design and duration of Part 2 will be similar to that for Part 1: a 3-day Screening period, Dosing on Day 1 (a single IV infusion of rezafungin) followed by five PK samplings between Day 1 and Day 8, and a Follow-up visit on Day 30 (\pm 5 days).

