9.2.10 Clinical Safety Laboratory Tests

See [Appendix 2](#) for the list of clinical laboratory tests to be performed and see [Table 1](#) and [Table 2](#) for the timing and frequency.

The Investigator must review the laboratory report, document this review, and record any clinically significant changes occurring during the study as an AE. The laboratory reports must be filed with the source documents.

Abnormal laboratory findings associated with the underlying disease are not considered clinically significant unless judged by the Investigator to be more severe than expected for the subject's condition.

All laboratory tests with values considered clinically significantly abnormal during participation in the study should be repeated until the values return to normal or baseline or are no longer considered clinically significant by the Investigator or medical monitor.

- If clinically significant values do not return to normal/baseline within a period of time judged reasonable by the Investigator, the aetiology should be identified, and the Sponsor notified.
- All protocol-required laboratory tests, as defined in [Appendix 2](#), must be conducted in accordance with the Laboratory Manual and the SoA ([Table 1](#) and [Table 2](#)).
- If laboratory values from non-protocol-specified laboratory tests performed require a change in subject management or are considered clinically significant by the Investigator then the results must be recorded.

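### Section 9's blood-volume limit equates 3% and 1% of body weight with 2.4 and 0.8 mL/kg, figures about 12-fold apart

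*Combined protocol and SAP*

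**What the plan says.** Section 9 (Study Assessments and Procedures) states the rule: "The blood volume for PK and other laboratory tests will not exceed the volume limits recommended by the EU paediatric guidance". A parenthesis then puts numbers on it: "up to approximately 3% of total weight [2.4 mL blood/kg body weight], with no more than 1% [0.8 mL blood/kg body weight", where the second limit applies to any single time. The base of the 1% is not repeated, so it is read here as the same base as the 3%.

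The next sentence of Section 9 sets a separate maximum for the youngest children: "For subjects <2 years of age (Group 4), a maximum total of 1 mL of blood will be taken for PK sampling". Section 9.3 repeats this and plans about 5 mL of PK blood (five samples of 1 mL) in Groups 1 to 3. The volume of a safety laboratory draw is not given anywhere.

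Other passages show that blood volume matters in Group 4. Table 2, footnote g, offers a way to save some: "Glucose can be measured by point-of-care testing to minimise the blood volume taken for the clinical laboratory tests". Section 9 allows repeat and unscheduled samples, and Section 9.2.10 asks for repeats: "All laboratory tests with values considered clinically significantly abnormal during participation in the study should be repeated until the values return to normal".

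**The concern.** The sentence treats a percentage of body weight and a volume per kg of body weight as equivalent. They are not, and the gap is far larger than the word for approximation in the sentence could cover.

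This sentence is the only stated cap on total study blood. Enrolment is from birth, and Section 6 sets no minimum weight; its only body-size criterion is a BMI range for children aged 2 years or more. The protocol expects very small children. Table 2 collects "Demographics (age, sex, race, gestational age, and birth weight" in Group 4, Appendix 5 has a row for premature infants, and Section 5.1 mentions children under 3 kg when it explains the lower-strength formulation. In such children the two readings give very different allowances, and a limit of this kind should have one meaning.

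**Working it through.** **Inputs.** From Section 9: 3% of weight, given as 2.4 mL/kg; 1%, given as 0.8 mL/kg. Assumed, because the documents do not give it: blood density between 1.00 and 1.06 kg/L. Example weight, also assumed: 3 kg.

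**Step 1. Try to reproduce the stated figures.** x% of weight is 10x g of blood per kg, so the volume is 10x / density mL/kg.

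| Limit | Percent of weight, in mL/kg | Bracketed figure | Ratio |
|---|---|---|---|
| Total, 3% | 30/1.06 = 28.3 to 30/1.00 = 30.0 | 2.4 | 28.3/2.4 = 11.8 to 30.0/2.4 = 12.5 |
| Single time, 1% | 10/1.06 = 9.43 to 10/1.00 = 10.0 | 0.8 | 9.43/0.8 = 11.8 to 10.0/0.8 = 12.5 |

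The stated equivalence is not reproduced. For 3% of weight to equal 2.4 mL/kg, blood would need a density of 30/2.4 = 12.5 kg/L, so the choice of density does not explain the gap.

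**Step 2. Convert the other way.** 2.4 mL/kg is 0.24% to 0.25% of body weight, and 0.8 mL/kg is 0.080% to 0.085%.

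**Step 3. Find the base that would make the brackets true.** 2.4/0.03 = 80 mL/kg and 0.8/0.01 = 80 mL/kg. Both brackets imply the same base of 80 mL/kg. The documents state no such base.

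**Step 4. Size in a small child (3 kg).**

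- By the brackets: 2.4 × 3 = 7.2 mL in total and 0.8 × 3 = 2.4 mL at one time.
- By percent of weight: 28.3 × 3 = 84.9 to 30 × 3 = 90 mL in total, and 9.43 × 3 = 28.3 to 10 × 3 = 30 mL at one time.

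**Step 5. Does planned PK blood exceed the stricter reading?** Against the bracketed total, 5 mL (Groups 1 to 3) fits at any weight above 5/2.4 = 2.1 kg, and 1 mL (Group 4) fits above 1/2.4 = 0.42 kg. Laboratory blood cannot be added to this check because its volume is not stated.

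**The case against.** The strongest reply is that this is a slip of wording with little practical effect. The rule is an upper bound. The brackets are explicit, in usable units and far below the percent-of-weight volumes, so a site that follows them satisfies both readings. The sentence defers to the EU guidance, and the parenthesis only restates it. The common base of 80 mL/kg also suggests one intended limit and not two rival ones. Exclusion criterion 4 removes children who are expected to become anaemic and not tolerate blood draws, and criteria 6, 7 and 9 narrow the intake of fragile neonates further.

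Most of this stands and keeps the point modest. It does not make the sentence correct. The guidance is not reproduced in the protocol, so a site that relies on the parenthesis has two incompatible restatements of it. The exclusions set no minimum weight. The 1 mL maximum in Group 4 does not help with total blood, because it covers PK samples only.

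A reader might also infer that the laboratory schedule cannot fit within the bracketed limit in a very small infant. The documents do not support that. It would need a panel volume, which they do not give, and the Synopsis allows the extent of Group 4 safety laboratory data to be adjusted after DSMB review 3.

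**Conclusion.** The point holds as an internal inconsistency in a safety limit. The percentages of weight are 11.8 to 12.5 times the mL/kg figures beside them, for both the total and the single-time limit. This rests on an assumed blood density of 1.00 to 1.06 kg/L and on reading the 1% on the same base as the 3%. No other passage resolves it.

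Two stronger conclusions might be inferred, and neither is supported. One is that the limit is unusable: the brackets are the stricter reading and can be followed as they stand. The other is that subjects will have too much blood taken: no planned draw is shown to exceed either limit, and nothing suggests that any site has used the larger figures.

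**What to change.** Reconcile the percentage wording and the mL/kg figures in Section 9 with each other and with the cited EU guidance, so that both describe the same limit. If percentages are kept, state what they are percentages of, for the total and for the single-time limit. This review does not say which figure is right.

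The cost is one sentence. Section 5.1 already plans an amendment after Part 1: "the study will be paused and a substantial amendment will be submitted to enable use of the paediatric formulation". The correction can go into it, ahead of Parts 2 and 3 and before Group 4 opens. Correcting the wording does not in itself change the PK schedule, the Group 4 PK maximum or any analysis.
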